8.7.2 Male subjects with partners who become pregnant

If a female partner of a male subject participating in this study becomes pregnant, the Investigator will ask the pregnant female partner to consent to be followed through to the end of her pregnancy and the neonate for 6 to 8 weeks after birth. This applies only to male subjects who receive the study drug.

After obtaining the necessary signed informed consent from the pregnant female partner directly, the Investigator will record pregnancy information on the Pregnancy Reporting form and submit it to the CRO Pharmacovigilance group within 24 hours of learning of the partner's pregnancy. The female partner will be followed to determine the outcome of the pregnancy. Information on the status of the mother and child will be forwarded to the Sponsor. Generally, the follow-up will be no longer than 6 to 8 weeks after birth. Any termination of the pregnancy will be reported regardless of fetal status (presence or absence of anomalies) or indication for the procedure.

9 SERIOUS ADVERSE EVENTS

9.1 Definition of Serious Adverse Event

An SAE is any event that meets any of the following criteria:

- Death
- Life-threatening
- Inpatient hospitalization or prolongation of existing hospitalization
- Persistent or significant disability/incapacity
- Congenital anomaly/birth defect in the offspring of a subject who received ABI-H2158
- Other: Important medical events that may not result in death, be life-threatening, or require hospitalization, may be considered an SAE when, based upon appropriate medical judgment, they may jeopardize the subject and may require medical or surgical intervention to prevent one of the outcomes listed in this definition. Examples of such events are:
 - Intensive treatment in an emergency room or at home for allergic bronchospasm
 - Blood dyscrasias or convulsions that do not result in inpatient hospitalization
 - Development of drug dependency or drug abuse

Definition of Terms

Life-threatening: An AE is life-threatening if the subject was at immediate risk of death from the event as it occurred; ie, it does not include a reaction that if it had occurred in a more serious form might have caused death. For example, drug induced hepatitis that resolved without evidence of hepatic failure would not be considered life-threatening even though drug induced hepatitis can be fatal.

Hospitalization: AEs requiring hospitalization should be considered SAEs. Hospitalization for elective surgery or routine clinical procedures that are not the result of AEs (eg, elective surgery for a pre-existing condition that has not worsened) need not be considered AEs or SAEs. If anything untoward is reported during the procedure, that occurrence must be reported as an AE, either “serious” or “non-serious” according to the usual criteria.

In general, hospitalization signifies that the subject has been detained (usually involving at least an overnight stay) at the hospital or emergency ward for observation and/or treatment that would not have been appropriate in the physician's office or outpatient setting. When in doubt as to whether “hospitalization” occurred or was necessary, the AE should be considered serious.

Disability/incapacitating: An AE is incapacitating or disabling if the experience results in a substantial and/or permanent disruption of the subject's ability to carry out normal life functions.

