6.1.2 Blinding

Study subjects, Investigators and other site personnel administering the study drug, performing the clinical assessments and handling data on the study subjects, will be blinded to individual subject treatments assignments (ie, ABI-H2158+ETV therapy or PBO+ETV therapy) throughout the duration of the study. Since decreases in HBV pgRNA may unblind site personnel, HBV pgRNA results will not be provided to sites until study completion.

A limited internal Sponsor team will be unblinded to individual subjects' treatment assignments throughout the study to ensure timely analysis of any emergent safety/tolerability issues, and completion of the prespecified safety data reviews that will be performed by the Data Review Committee (DRC) (see [Section 10.6](#)). The unblinded individuals will be identified in the DRC Charter along with their specific roles and responsibilities. All other Sponsor personnel will remain blinded until completion of the study. The contract research organization's (CRO's) Medical Monitor may be unblinded to individual subjects' treatment assignments where required for assessment of emergent safety/tolerability issues.

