6.1.2.1 Unblinding in Emergency Situations

Requests can be made to unblind an individual study subject for emergencies or urgent situations. Prior to unblinding, and if the situation permits, the Investigator should first contact the Sponsor and/or authorized Medical Monitor to discuss the case. However, the final decision whether to unblind a subject will be the Investigator's decision, and the Investigator need not wait for the unblinding permission to be granted by the Sponsor/CRO Medical Monitor in emergency situations where identification of the individual treatment assignment is required for the immediate medical management of the subject. Access to the unblinded treatment assignment should be limited to the minimum number of people required for emergent management of the subject. The actual treatment assignment must not be disclosed to the subject and/or other study personnel, including site monitors, office staff; nor should there be any written or verbal disclosure of the code in the subject's study documents.

The request for unblinding should include the protocol number, site number, subject identifier (eg, subject number), treating Investigator's contact info, a detailed reason for the unblinding, and date the

information is needed. All key correspondence between the requestor and Sponsor or CRO Medical Monitor should be saved in the Trial Master File (TMF).

The IRT system will be used as the unblinding tool. In the event that an individual subject's treatment assignment is unblinded, the date and reason that the blind was broken must be recorded in the source documentation and case report form, as applicable. Any treatment assignments that are unblinded must be immediately reported to the CRO Medical Monitor and the Sponsor. Code-break IRT access is given to the Investigator/designated person at the site and to the designated Medical Monitor(s) for the study.

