10.2 Sample Size Determination

Forty treatment-naïve subjects with HBeAg positive CHB will be enrolled in Cohort 1 and 40 treatment-naïve subjects with HBeAg negative CHB will be enrolled in Cohort 2. Subjects will be randomized to receive either placebo or 300 mg ABI-H2158 in a 1:3 ratio. That is, in Cohort 1 and in Cohort 2, 10 subjects will be randomized to treatment with placebo, and 30 subjects will be randomized to treatment with ABI-H2158. This sample size is not based on statistical considerations but is adequate for a proof-of-concept study.

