7.1.4. Serious Adverse Events

Serious adverse events (SAEs) will be identified and captured as SAEs if the AEs met protocol-specified definitions of a SAE.

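### The birth-defect SAE criterion in protocol 9.1 names ABI-H2158 instead of study drug, so as written it omits PBO+ETV offspring and blinded investigators cannot tell whether it applies

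*Combined protocol and SAP*

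**What the plan says.** Protocol 9.1 opens its list with "An SAE is any event that meets any of the following criteria", so one criterion is enough. Death, life-threatening events, hospitalization and disability are listed without reference to treatment. The congenital criterion is different: "Congenital anomaly/birth defect in the offspring of a subject who received ABI-H2158". A last, discretionary criterion begins "Important medical events that may not result in death, be life-threatening, or require hospitalization, may be considered an SAE when" and leaves the decision to medical judgment.

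On blinding, protocol 6.1.2 states that subjects, investigators and other site personnel "will be blinded to individual subject treatments assignments (ie, ABI-H2158+ETV therapy or PBO+ETV therapy) throughout the duration of the study". Section 6.1.2.1 provides the code-break: "Requests can be made to unblind an individual study subject for emergencies or urgent situations". Deciding whether an event is serious is not mentioned there as a reason.

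Protocol 9.2 requires SAEs to be reported within 24 hours of the site learning of them. SAP 7.1.4 takes the definition over from the protocol: SAEs "will be identified and captured as SAEs if the AEs met protocol-specified definitions of a SAE".

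**The concern.** A seriousness rule should give the same answer for the same event in either arm, and the person applying it should be able to apply it without knowing the assignment. This criterion fails on both counts.

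Control subjects are not unexposed. They take ETV, which the protocol treats as a study drug. Protocol Appendix 3 also states that embryofetal studies of ABI-H2158 have not been done, so this is an outcome for which even-handed collection in the comparator matters.

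At stake is whether a birth defect is automatically serious, and so reported within 24 hours, or whether that is left to another criterion or to a site's guess about treatment.

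**Working it through.** No formula applies. The check is a reading of the sections against each other.

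1. **Who the criterion covers.** Receipt of ABI-H2158 is a condition. Allocation in each cohort is given in protocol 10.2: "10 subjects will be randomized to treatment with placebo, and 30 subjects will be randomized to treatment with ABI-H2158". Over two cohorts, 10 + 10 = 20 of 40 + 40 = 80 planned subjects are on PBO+ETV and fall outside the wording. This is a count of subjects, not of events.

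2. **Whether another section extends it.** None does. No section tells sites to treat every subject as exposed for this purpose.

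3. **Whether the pregnancy section fills the gap.** Protocol 8.7.1 follows any pregnant female subject and her neonate for 6 to 8 weeks after birth. It makes spontaneous abortion and stillbirth SAEs in all cases, and has pregnancy complications and medically indicated terminations reported as an AE or SAE. It does not name a birth defect in a live-born child. Its rule for post-study reports covers pregnancy-related SAEs, so it relies on the definition in 9.1.

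4. **Whether the wording matches the rest of the documents.**

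| Place | Term used |
|---|---|
| Protocol 4.3 and 6.5 | study drug, meaning ABI-H2158 or PBO, and ETV |
| Protocol 8.7.1 and 8.7.2 | study drug(s), no arm named |
| SAP 3.6.1 | study drug, meaning ABI-H2158 or matching PBO, and ETV |
| Protocol 9.1, congenital criterion | ABI-H2158 only |

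5. **Whether a site can apply it.** The investigator must start the 24-hour report but is blinded (6.1.2), and the code-break in 6.1.2.1 is provided for emergencies and urgent situations. A site that sensibly reports every birth defect is following a rule that the protocol does not contain.

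6. **Whether it reaches the analysis.** SAP 7.1.6 tabulates treatment-emergent SAEs by arm, and off-treatment events in similar categories. A pregnant female subject stops study drug at once (8.7.1), and the treatment-emergent window closes 28 days after ABI-H2158/PBO stops (SAP 7.1.5.1). AEs are recorded only to the end of follow-up (8.1), which is 24 weeks by protocol and 12 weeks after the early termination (SAP 1.2). A defect found at a term birth would therefore generally fall outside the treatment-emergent window, and often outside AE collection, in both arms. Prenatal diagnoses could fall inside. So could births to partners of male subjects, for whom 8.7.2 sets no stopping rule during the 72 planned weeks.

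**The case against.** The strongest case against is that the wording has almost no consequence, and much of that case stands.

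- **Other criteria remain.** A reader might infer that a birth defect in the control arm could never be an SAE. The documents do not support that: any one criterion suffices, so the event could qualify through death, threat to life, hospitalization, disability or the important-medical-event clause. Those routes are narrower or discretionary, whereas the congenital criterion is meant to make the event serious automatically.
- **Blinding works against selective loss.** A reader might infer that the by-arm SAE comparison is one-sided. But blinded sites cannot selectively leave out PBO events. If they report every birth defect, capture is equal; if they hesitate, they hesitate in both arms. SAP 7.1.4 has no step that reclassifies events by arm after unblinding.
- **The allocation share is not a loss rate.** A reader might turn 20 of 80 subjects into a quarter of events lost. That only restates the 3:1 allocation. It would need arm-dependent capture and equal risk in the two arms, neither of which the documents give.
- **Pregnancy surveillance covers both arms.** Pregnancies are reported within 24 hours under 8.7 whatever the arm, with partner follow-up subject to consent. A control-arm outcome would probably reach pharmacovigilance. That narrows the practical gap but does not make a live-born defect an SAE.

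None of this makes the wording right. It limits what can be claimed from it.

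**Conclusion.** The point holds as a defect in an operative safety rule. Read literally, the criterion omits offspring of PBO+ETV subjects and depends on a fact the investigator is not meant to know.

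Its size is minor. Pregnancy is excluded at entry, dual contraception is required, only 20 control subjects were planned, and development was discontinued on 01 September 2021. The expected number of events is very small; the documents give no rate from which to calculate it. The benefit is equal reporting that sites can carry out.

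The conclusion assumes that no site instruction outside these documents already tells investigators to treat every subject as exposed.

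**What to change.** In protocol 9.1, replace the restriction to recipients of ABI-H2158 in the congenital criterion with *who received study drug (ABI-H2158 or PBO, and/or ETV)*. This agrees with 4.3, 6.1.2 and 8.7.

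No separate phrase for partners is needed. The offspring of a subject already include children fathered by male subjects, and an added partner phrase could be read as requiring the partner's own exposure.

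The cost is one phrase. It adds no visit or data item, and SAP 7.1.4 needs no edit because it refers back to the protocol. As the study has ended early, a clarification letter of the kind already issued could cover any pregnancy still being followed, and the present wording should not be carried into other protocols.

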9.2 Reporting Serious Adverse Events

All SAEs must be reported within 24 hours of learning about the event using the SAE Report form to the CRO Pharmacovigilance group. The initial report should be promptly followed by detailed, written reports, which will include copies of relevant hospital case reports, autopsy reports, and other documents when requested and applicable. This additional information will be requested, if necessary, by the responsible monitor within 5 days of receipt of the alert report. This is to ensure that the initial reporting of SAEs is made to the Health Authorities within the required time period.

For a follow-up report to the authorities, the monitor may be required to collect further information for a final evaluation of the case. Reporting to the respective country Health Authorities will be the responsibility of the Sponsor and the CRO.

The CRO will be responsible for informing all central Institutional Review Boards (IRBs)/ Independent Ethics Committees (IECs) of SAEs as required. It will be the responsibility of the individual investigators to inform any local IRBs/IECs of SAEs as required. Correspondence with the IRB(s)/IEC(s) relating to the reporting of SAEs will be retained in the study file.

9.3 Overdose

An overdose is defined as the accidental or intentional administration of any dose of a product that is considered both excessive and medically important. The Medical Monitor may be contacted for questions concerning potential cases of overdose. An overdose is not in and of itself considered to be an AE unless it results in untoward medical effects. Any AE associated with an overdose or incorrect administration of study drug should be entered in the subject's source documentation and Adverse Event eCRF. If the associated AE fulfills the criteria of an SAE, then the event should be reported to the Sponsor or CRO within 24 hours after the site learns of the event.

9.4 Management of ALT Elevations

All subjects participating in the study will be closely monitored for ALT elevations and/or signs of potential decline in hepatic function (see [Figure 2](#)). Subjects experiencing ALT elevations $\geq 2 \times$ Baseline (Day 1) or on-treatment nadir and $> 2 \times$ ULN during study treatment or during post-treatment follow-up should be closely monitored with regular Unscheduled Visits every 1-2 weeks at the discretion of the Investigator. At these visits, the following laboratory tests will be performed: ALT, AST, total bilirubin (if total bilirubin is elevated, reflex to direct bilirubin), serum albumin, INR and creatine kinase. The Investigator will determine if other Unscheduled Visit assessments should be performed. Additionally, the following guidance is provided for management of subjects with ALT elevations:

- ALT Elevation without Declining Hepatic Function
 - All subjects with an ALT elevation on treatment, defined as ALT $> 2 \times$ Baseline or on-treatment nadir and $\geq 10 \times$ ULN, should have the ALT findings confirmed within 3 days of receipt of the original results. All subjects should return for an Unscheduled Visit ([Section 7.6](#)).
 - If the ALT elevation is confirmed, then an additional Unscheduled Visit will be performed to further evaluate the subject. At this visit, the following laboratory tests will be performed: ALT, AST, total bilirubin (if total bilirubin is elevated, reflex to direct bilirubin), serum

albumin, INR, creatine kinase, HBV DNA, quantitative HBV serologies (HBeAg [reflex qualitative HBeAg if quantitative HBeAg is negative] and HBsAg [reflex qualitative HBsAg if quantitative HBsAg is negative]), HAV IgM, HCV RNA, HDV RNA, and HEV IgM. The Investigator will determine if other Unscheduled Visit assessments should be performed.

- If an intercurrent cause is determined to be causal, subjects with an ALT elevation without declining hepatic function and without contraindications may continue treatment and the intercurrent illness should be treated as deemed medically appropriate by the Investigator.
- Subjects with an ALT elevation without declining hepatic function and without contraindications may continue treatment with study drug under close observation.
 - If ALT is rising at the confirmatory visit, subjects should return for an Unscheduled Visit every 2 to 5 days until the ALT elevation has stabilized. At these visits, the following laboratory tests will be performed: ALT, AST, total bilirubin (if total bilirubin is elevated, reflex to direct bilirubin), serum albumin, INR, creatine kinase, HBV DNA, quantitative HBV serologies (HBeAg [reflex to qualitative HBeAg if quantitative HBeAg is negative] and HBsAg [reflex to qualitative HBsAg if quantitative HBsAg is negative]). The Investigator will determine if other Unscheduled Visit assessments should be performed. Subjects whose ALT has stabilized should continue to be monitored weekly (or more frequently, as deemed necessary by the treating physician) until ALT values return to normal or Baseline levels.
- ALT Elevation with Declining Hepatic Function
 - Subjects with confirmed ALT elevation with evidence of declining hepatic function should be discontinued from study treatment. This is defined as:
 - ALT elevation $\geq 2 \times$ Baseline (Day 1) or nadir and $> 2 \times$ ULN AND
 - Direct bilirubin increase to $\geq 2 \times$ Baseline (Day 1) and $\geq 2 \times$ ULN OR
 - Albumin decline ≥ 0.5 g/dL OR INR $> 2 \times$ Baseline (Day 1) OR
 - Symptoms of liver inflammation (eg, fatigue, weakness, lack of appetite, nausea, vomiting, jaundice or discolored feces)
 - Subjects with evidence of declining hepatic function should return for an Unscheduled Visit every 2 to 5 days until the relevant laboratory values stabilize. Subjects whose hepatic function has stabilized should continue to be monitored weekly (or more frequently as deemed necessary by the Investigator) until the relevant laboratory values return to normal or Baseline (Day 1).

[figure not shown]
All subjects with ALT elevation with or without declining hepatic function should continue to be followed on their regular study visit schedule, with the addition of Unscheduled Visits as described above. If the post-treatment ALT elevation has not substantially resolved by the last study follow-up visit, subjects should continue to return to clinic as deemed medically appropriate by the Investigator, in consultation with the Sponsor. The Unscheduled Visit module in the case report form should be utilized as needed to gather additional clinical and laboratory data until the ALT elevation is documented to be

either resolved or resolving (defined as consistent ALT declines of 10% or more or normalization of ALT) on at least 2 successive visits.

If 2 or more subjects meet these ALT elevation management criteria, the US FDA and other relevant regulatory agencies will be notified, and subsequent steps will be determined after consultation with these agencies.

Following cessation of study drug treatment under this protocol, all subjects will be closely followed for ALT elevations and/or signs of potential decline in hepatic function. This applies to all subjects whether they prematurely discontinue study drug or complete the study treatment per protocol. Any subject with a post-treatment ALT elevation without evidence of declining hepatic function or a post-treatment ALT elevation with evidence of declining hepatic function as defined above, will be evaluated as noted above.

Figure 2: Management of ALT Elevation

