7.8.6 Clinical Laboratory Tests

Clinical laboratory tests will be performed at the designated Central laboratories at the timepoints indicated in the Schedule of Assessments table in [Appendix 1](#). Should any laboratory parameter require urgent testing to support immediate medical care of a subject, samples should be collected for both local and central laboratory assessment. The local result may be used to manage the emergent medical situation, however only the results from the central laboratory will be reported in the study database for analysis purposes.

The specific components of the clinical laboratory tests are listed below in [Table 5](#).

Table 5: Clinical Laboratory Tests

Panel	Tests
Clinical Chemistry	Blood glucose levels, serum or plasma electrolytes (sodium, potassium, chloride, bicarbonate), calcium, creatine kinase, blood urea nitrogen, creatinine, uric acid, total and direct bilirubin ^a , ALT, AST, GGT, alkaline phosphatase, LDH, amylase, triglycerides, total cholesterol, inorganic phosphate or total phosphate, total protein, albumin, lipase, and total serum or plasma globulins
In case of ALT Elevation	ALT, AST, total bilirubin, serum albumin, creatine kinase, and INR
Hematology	Complete blood counts: hemoglobin, hematocrit, RBC indices (MCV, MCHC), reticulocyte counts, leukocyte counts (total and differential), and platelet counts

Panel	Tests
Coagulation	Prothrombin time/INR and aPTT
Urinalysis	pH, specific gravity, protein, glucose, ketones, and occult blood
Other	AFP, HbA1c, and FSH (ALL Females regardless of fertility status)
Pregnancy tests	For females only; a serum pregnancy test must be performed at Screening. On Day 1, urine and serum pregnancy test should be performed predose. Subject may begin treatment based on urine results. Any subject negative by urine subsequently found to be positive on serum should immediately discontinue treatment. All post-Day 1 pregnancy tests may be conducted by urine dipstick. If positive on dipstick, reflex to serum. A positive result disqualifies the subject for study treatment.
Urine drug Screening	Amphetamine/methamphetamine, barbiturates, benzodiazepines, cocaine metabolite, ethanol, opiates, phencyclidine, and propoxyphene.
Antibodies	HCV, HDV, HAV IgM, HEV IgM, and HIV

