AFP: alpha fetoprotein; ALT: alanine aminotransferase; aPTT: activated partial thromboplastin time; AST: aspartate aminotransferase; FSH: follicle-stimulating hormone; GGT: gamma-glutamyl transpeptidase; HAV: hepatitis A virus; HbA1c: hemoglobin A1c; HCV: hepatitis C virus; HDV: hepatitis D virus; HEV: hepatitis E virus; HIV: human immunodeficiency virus; IgM: immunoglobulin M; INR: International Normalized Ratio; LDH: lactate dehydrogenase; MCHC: mean corpuscular hemoglobin concentration; MCV: mean corpuscular volume; RBC: red blood cell; ULN: upper limit of normal.

^a Perform fractionated bilirubin if total bilirubin >ULN.

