PK Sample Collection																					
Pre-dose ⁱ		X		X											X						X
Postdose: 30 min to 2 hours			X		X	X			X	X											
Postdose: 2 to 4 hours		X																			
Postdose: 4 to 6 hours							X	X													
Pharmacogenomic sample		X																			

Period or Visit	Follow-Up				ALT Elevation ^k	Premature Termination ^j	Unscheduled ^k
	4 Wks Post	8 Wks Post	12 Wks Post	24 Wks Post			
Study Day or Week							
Visit Window (days)	±5	±5	±5	±5	NA	NA	NA
Complete physical exam ^c				X		X	
Symptom-directed physical exam	X	X	X				X
12-lead ECG ^d				X		X	
Weight				X			
Vital signs	X	X	X	X		X	X
Concomitant medications and adverse events	X	X	X	X		X	X
Dosing diary						X	
Study drug accountability ^e	X	X	X	X		X	
Study drug dispensation ^e	X		X				
HBV DNA	X	X	X	X	X	X	X
HBsAg, HBeAg ^f	X	X	X	X	X	X	X
HBcrAg	X	X	X	X		X	X
HBsAb, HBeAb				X		X	
HBV pgRNA	X	X	X	X		X	X
Sample for HBV DNA sequencing and HBV nucleic acids	X	X	X	X		X	X
ALT, AST, total bilirubin, serum albumin, creatine kinase, & INR					X		
HAV (IgM), HCV RNA, HDV RNA, HEV (IgM)					X		
Chemistry	X	X	X	X		X	X
Hematology	X	X	X	X		X	X
Coagulation	X	X	X	X		X	X
Urinalysis	X		X	X		X	X
Urine drug test						X	X
Pregnancy test ^h	X					X	X
PK sample collection	X					X	X

PBO: placebo; ECG: electrocardiogram; ETV: entecavir; FSH: follicle-stimulating hormone; HAV: hepatitis A virus; HBcAb: antibody to the HBV core antigen; HBcrAg: hepatitis B core-related antigen; HBeAb: HBeAg antibody; HBeAg: hepatitis B “e” antigen; HBsAb: HBsAg antibody; HBsAg: hepatitis B surface antigen; HBV: hepatitis B virus; HCV: hepatitis C virus; HDV: hepatitis D virus; HEV: hepatitis E virus; HIV: human immunodeficiency virus; IgM: immunoglobulin M; IRT: Interactive Response Technology; NA: not applicable; PK: pharmacokinetic.

^a In addition to the study specific Main Informed Consent Form, a separate consent is required for optional pharmacogenomic sampling.

- b Liver staging is to be performed to determine lack of cirrhosis or advanced liver disease as required by inclusion criteria.
- c Examination of the breasts and genitalia are not required unless indicated.
- d During the study, any clinically significant ECG result should be confirmed, and if confirmed, should be recorded as an AE.
- e Study drug dispensation from Week 72 onwards and drug accountability from 4 weeks post treatment onwards only applies to ETV therapy; ETV will be continued throughout the 24-week follow-up period.

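### Direct bilirubin is ordered only when total bilirubin is elevated, yet the only bilirubin stop-treatment limb needs a direct value on Day 1 and at the ALT-elevation visit

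*Combined protocol and SAP*

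**What the plan says.** Protocol Section 9.4 lists the tests for ALT-elevation visits in three places: the close-monitoring visits, the further visit once an on-treatment elevation of at least 10 x ULN is confirmed, and the repeat visits every 2 to 5 days while ALT is rising. All three order "total bilirubin (if total bilirubin is elevated, reflex to direct bilirubin", so direct bilirubin depends on the total result.

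The other listings agree with that or are narrower:

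- Table 5 (Section 7.8.6), ALT-elevation row: "ALT, AST, total bilirubin, serum albumin, creatine kinase, and INR".
- Appendix 1, ALT Elevation column: "ALT, AST, total bilirubin, serum albumin, creatine kinase, & INR". Chemistry is not ticked in that column.
- Table 5, chemistry row: "total and direct bilirubin", with footnote a attached: "Perform fractionated bilirubin if total bilirubin >ULN".

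The stop-treatment definition in Section 9.4 takes an ALT condition (at least 2 x Day 1 or nadir, and above 2 x ULN) and adds a bilirubin, albumin, INR or symptom limb. The bilirubin limb begins "Direct bilirubin increase to" and sets two thresholds, at least 2 x Day 1 and at least 2 x ULN. Total bilirubin does not appear in it. For those who do not meet the definition, Section 9.4 says: "Subjects with an ALT elevation without declining hepatic function and without contraindications may continue treatment with study drug under close observation". SAP Section 7.2.2.2 tabulates the same criterion.

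**The concern.** A stop rule is only as good as the measurement that feeds it. Here the written test rule does not secure the value that the written stop criterion needs, at either end of the comparison. The Day 1 reference may never have been measured, and the on-treatment value may not be measured because a different analyte is still in range. A site following Section 9.4 to the letter could then class a subject as having no decline in hepatic function and continue study drug. The SAP count would inherit the same missing values. The sponsor ended development over ALT elevations consistent with drug-induced liver injury (SAP Section 1), so complete hepatic-function data matter.

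**Working it through.** The plan gives no figure to reproduce, so the check is an inequality.

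Notation: D = direct bilirubin, T = total bilirubin, Ud and Ut = their ULNs, B = direct bilirubin on Day 1. The rules come from Section 9.4 and Table 5 footnote a. Neither ULN is in the documents.

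**On-treatment value**

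1. No reflex test is run if T <= Ut.
2. The limb is met if D >= 2 x Ud and D >= 2 x B.
3. Direct bilirubin is part of the total, so D <= T.
4. The limb is therefore met untested only if 2 x Ud <= D <= T <= Ut (with B <= D/2). This has a solution exactly when Ud/Ut <= 1/2.
5. At a ratio of exactly 1/2 the only solution is D = T = Ut, with all bilirubin direct. Above 1/2, anyone who meets the limb has T > Ut and is reflexed. A grid check agreed: 1326, 630, 1 and 0 qualifying points at ratios 0.25, 0.33, 0.50 and 0.51.

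The untested band for D runs from 2 x Ud to Ut. With assumed ULNs in mg/dL:

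| Ud | Ut | Ud/Ut | 2 x Ud | Untested D | Smallest direct share when T = Ut |
|---|---|---|---|---|---|
| 0.2 | 1.2 | 0.17 | 0.4 | 0.4 to 1.2 | 0.4/1.2 = 33% |
| 0.3 | 1.2 | 0.25 | 0.6 | 0.6 to 1.2 | 0.6/1.2 = 50% |
| 0.4 | 1.0 | 0.40 | 0.8 | 0.8 to 1.0 | 0.8/1.0 = 80% |
| 0.5 | 0.9 | 0.56 | 1.0 | none (1.0 > 0.9) | not applicable |

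**Day 1 value**

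1. Under footnote a, a subject with Day 1 total at or below ULN is not fractionated, so B is missing. This does not depend on Ud/Ut.
2. Exclusion 13c bars total bilirubin above 1.2 x ULN at Screening, apart from Gilbert's syndrome, so a normal Day 1 total should not be unusual. The documents give no count.
3. If B <= Ud, then D >= 2 x Ud already gives D >= 2 x B, and the missing value changes nothing. It matters only if B > Ud.
4. Exclusion 13d bars direct bilirubin above 1.2 x ULN at Screening. If 13d was applied and Day 1 was no higher than that limit, then 2 x B is at most 2 x 1.2 = 2.4 x ULN. The baseline part could then change the answer only for D from 2.0 up to 2.4 x ULN.
5. SAP Section 3.6.2 would let a Screening value stand in as baseline for analysis. Section 9.4, which governs stopping, names Day 1.

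If direct bilirubin is measured whatever the total, both gaps close for every ratio of the two ULNs.

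**The case against.** The strongest reply is that direct bilirubin was probably run routinely. ALT-elevation visits are Unscheduled Visits, Section 7.6 makes chemistry a minimum there, and the chemistry row names direct bilirubin. Exclusion 13d needs a direct value whatever the total. SAP Section 3.4 has a rule for direct values below 0.1 mg/dL, which would be less expected if only samples with high total were fractionated. This may describe practice, and the Laboratory Manual and Figure 2, which might settle it, are not available. It does not remove the conflict in the text. Footnote a qualifies that same chemistry row, and Section 9.4 lists its own tests and then says "The Investigator will determine if other Unscheduled Visit assessments should be performed".

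The second reply is that many conditions must coincide: a ULN ratio of one half or less, total still in range, direct bilirubin at least doubled, no albumin or INR trigger, no symptoms (fatigue and nausea count), and no test added by the Investigator. That stands. If total later passes its ULN, the reflex fires at the next visit, so the likely harm is delay. Such visits come every 2 to 5 days while ALT is rising on the 10 x ULN pathway, but every 1 to 2 weeks, at the Investigator's discretion, at the lower ALT threshold.

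A reader might infer three stronger things that the documents do not support:

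- That subjects were in fact kept on drug with an unmeasured stop criterion. Nothing shows this.
- That Section 9.4 is the only route to stopping. Section 7.9 allows withdrawal for safety by the Investigator or Sponsor, and Section 7.9.1 covers discontinuation for adverse events and for confirmed hepatic decline.
- That exclusion 13d could not be checked at Screening. Because 13d itself demands a direct value, it is better read as a sign of routine testing.

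**Conclusion.** The point holds as an inconsistency between the written test rule and the written stop criterion.

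- The possible lack of a Day 1 direct value follows from footnote a whatever the ULNs. Its effect on decisions is probably small: it needs a Day 1 direct value above ULN, and direct bilirubin between 2.0 and 2.4 x ULN if the 13d limit still applied on Day 1.
- The untested on-treatment limb exists only if the direct ULN is at most half the total ULN. That is an assumption. Across the assumed ULNs the band runs from 0.4 to 1.2 mg/dL at its widest to none.

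Frequency is unknown. Albumin, INR, symptoms and Investigator or Sponsor discretion are real but partial safeguards. Priority is low for this trial: development stopped on 01 September 2021 and follow-up was set at 12 weeks after the last dose (SAP Sections 1 and 1.2). What remains is the classification of ALT elevations in follow-up, which Section 9.4 also covers, and reuse of the text in a later protocol.

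**What to change.** - Delete the reflex condition in its three places in Section 9.4, and delete Table 5 footnote a.
- Add direct bilirubin to the ALT-elevation panel in Table 5 and Appendix 1.
- State that direct bilirubin is measured at Screening, Day 1 and every ALT-elevation visit regardless of total.

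The cost is one more analyte on blood already drawn and a few more flags to review. If the laboratory already ran the test routinely, the edit only makes the text say so.

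Optionally, SAP Section 7.2.2.2 could report by arm how many Safety Analysis Set subjects had no postbaseline direct bilirubin, with a matching footnote in the Section 7.2.1.2 table. This is a reporting preference: Section 7.2.1.2 already uses per-test denominators and plans a listing of results. It needs no further dosing and costs one sentence and one footnote.
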